4. ANALYSIS SETS/POPULATIONS/SUBGROUPS

Participants

The study population is derived from the Aetna Commercial Fully Insured and Medicare populations. From this population, specific characteristics associated with an increased proportion of prevalent atrial fibrillation are identified through claims data to identify a population at increased risk for undiagnosed atrial fibrillation based on International Classification of Diseases Ninth (ICD-9) and Tenth (ICD-10) revisions diagnoses in the Aetna Claims Database or Aetna Health Analytics Profile Database (HPD):

Inclusion Criteria:

- Male age > 55 years, or females age > 65 years, and
- Prior CVA, or
- Heart failure, or
- Diagnosis of both diabetes and hypertension, or
- Mitral valve disease, or
- Left ventricular hypertrophy, or
- COPD requiring home O2, or
- Sleep apnea, or
- History of pulmonary embolism, or
- History of myocardial infarction, or
- Diagnosis of obesity

Exclusion Criteria:

- Current or prior diagnosis of atrial fibrillation, atrial flutter or atrial tachycardia
- Receiving chronic anticoagulation therapy
- Hospice care
- End stage renal disease
- Diagnosis of moderate or greater dementia
- Implantable pacemaker and/or defibrillator
- History of skin allergies to adhesive patches

Eligible Aetna members will be contacted by letter, electronically or paper, with information about the study and an invitation to learn more via a study-specific web site as well as the option to discuss with a research coordinator. Once an individual agrees to participate they will be directed to an online Informed Consent Document, or if they prefer, one will be mailed to them.

A conservative estimate is that 5% of the approached population will agree to participate in the study. With an estimated >100,000 eligible participants to approach this should allow for the recruitment of a total of 2,000 individuals for randomization and allow for development of a matched observational cohort of 4,000 individuals.

It is anticipated that 10,000 invitations will be sent out to eligible Aetna members on a rolling basis every one to two weeks with invitations continuing until ~2,100 (to account for an assumed 5% drop-out in first year) individuals have agreed to participate and signed the informed consent.

Randomized Controlled Trial Population: Immediate Monitoring (Intervention Group) vs. Delayed Monitoring (Control Group)

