6. HANDLING OF MISSING DATA

Missing data will be quantified for all variables. Given that endpoints are based on claims data, endpoints that do not appear in the claims data are measured as zero or absent and are thus not considered missing during the time that the subject remains enrolled in Aetna. Medical and pharmacy coverage will be assessed to identify truly missing data from zero/absent. For time to event analyses, subjects are censored at time of disenrollment. In addition, age and sex were included in the inclusion criteria for all subjects, and thus are not anticipated to be missing. Patterns of missing-ness of other covariates will be assessed by determining bivariate associations of the missing data (have data/do not have data) with demographic variables and co-morbidity scores. Variables found to be significantly associated with missing data will be used as covariates in the multivariable models used for the primary and secondary endpoints.

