7. STATISTICAL METHODOLOGY

Sample Size Determinations

For the 4-month RCT, the sample size of 1,000 subjects for each group (immediate monitoring = active monitoring and delayed monitoring=no active monitoring) achieves >99% power to find a difference between an expected incident atrial fibrillation rate of 5% in the active monitoring group and an expected incident atrial fibrillation rate of 0.5% group without active monitoring with a two-sided alpha of 0.05. This sample size also achieves adequate power for the detection of the difference between the two groups at lower event rates, achieving 98% power for an expected rate of 2% in the active monitoring group and 0.1% in the delayed monitoring group with a two-sided alpha of 0.05.

For the Matched Observational Cohort Study, at 12 months, sample sizes of 2,000 subjects in the active monitoring group (immediate monitoring + delayed monitoring) and 4,000 subjects in the matched control group achieves >99% power to find a difference in the expected atrial fibrillation rate of 7% in the active monitoring group and 2% in the matched control group with a two-sided alpha of 0.05.

For the Matched Observational Cohort Study, based on an expected prevalence of atrial fibrillation of 10% in both the actively monitored (i.e., n=200) and matched control cohorts (i.e, n=400), a 7.5% event rate/year in the matched observational cohort and a 50% reduction in events in the actively monitored cohort due to earlier diagnosis prior to having an event or symptom, the expected combined event rate is 5% in the actively monitored subjects and 12% in the matched observational controls. Given these assumptions, the sample size yields 81% power to detect the expected difference in time to event with a log rank test with a two-sided alpha of 0.05.

Descriptive Statistics

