The primary analysis will compare the proportion of subjects newly diagnosed with atrial fibrillation (numerator) per number of total number of subjects in the randomized group (denominator) during the first 4 months of the study between the immediate monitoring (intervention group) and delayed monitoring (control) groups using Fisher's exact test. Multivariable analysis of the primary outcome will also be performed using binomial multivariable logistic regression models to include baseline demographic (age, sex, race/ethnicity, median household income, geography, insurance type), and co-morbidity covariates. The primary analysis will be conducted with the endpoint (AF/atrial flutter) defined by any event in the Aetna databases with the ICD-9/ICD-10 code for AF/atrial flutter. Secondary analysis will be conducted using the same methods with the AF/atrial flutter endpoint defined by the HPD.

Intention-to-treat analysis will include all subjects who were randomized to the immediate monitoring or delayed monitoring groups and follow-up for outcomes from the device and the Aetna databases will be from date of enrollment to time of completion of monitoring with final patch or 4 months following enrollment, whichever is longest.

A per-protocol analysis will also be performed which will be limited to subjects in the immediate monitoring group who has a Zio patch reading of a total of at least 30 minutes and all subjects randomized to the delayed monitoring group.

Analysis of Matched Observational Cohort Study—12 month Follow-up

Analyses for the Matched Observational Cohort Study will involve comparison of outcomes in the actively monitored group from the randomized controlled trial (intervention = exposure to Zio patch monitoring) and the matched controls. Analysis at 12-month follow-up will include

the outcomes of new atrial fibrillation diagnosis and new prescriptions for 1) anticoagulants and 2) other AF-related medications.

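### The supportive adjusted logistic model of the 4-month AF outcome is sparse, with no fallback if controls have no events; Fisher's primary test is unaffected

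*SAP*

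**What the plan says.** SAP Section 7 (Sample Size Determinations) plans on "the sample size of 1,000 subjects for each group" and, for immediate monitoring, on an "expected incident atrial fibrillation rate of 5% in the active monitoring group". For the delayed arm it takes 0.5%, and the comparison is made "with a two-sided alpha of 0.05". It also vouches for a lower-rate case, "achieving 98% power for an expected rate of 2% in the active monitoring group and 0.1% in the delayed monitoring group".

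Under Analysis of Randomized Controlled Trial, the primary analysis compares the two proportions by Fisher's exact test. The same outcome is then also analysed with "binomial multivariable logistic regression models to include baseline demographic (age, sex, race/ethnicity, median household income, geography, insurance type), and co-morbidity covariates", and the methods are repeated for the HPD definition of AF. The co-morbidity covariates are not listed or capped, and no method for sparse data is given. Section 8 (Sensitivity Analyses) deals only with Cox models in the matched cohort.

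The covariate list in Section 5 holds five co-morbidity scores (CHA2DS2-VASc, two Episode Risk Group scores, Charlson, Framingham) and 26 baseline diagnoses. Section 6 tests missingness of covariates against demographic variables and co-morbidity scores, and then: "Variables found to be significantly associated with missing data will be used as covariates in the multivariable models", for primary and secondary endpoints. It states neither imputation nor a missing category.

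**The concern.** Ordinary maximum-likelihood logistic regression needs enough events, in both arms, for the number of terms it carries. Here the control arm is expected to supply about five. Two problems can follow: an odds ratio that tends to be too large, and, if no control has an event, an odds ratio that is infinite whatever covariates are used. The second matters because the SAP presents a scenario with one expected control event as adequately powered.

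The covariate set is also open. Co-morbidity covariates may mean the five scores or may take in the 26 diagnoses, and the missingness rule lets the observed data decide some of the terms. Settling this after outcomes are known would be discretionary. At stake is the adjusted result reported beside the primary test, not the primary test itself.

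**Working it through.** **1. The plan's power, reproduced.** With n = 1,000 per arm and the pooled normal approximation,
power = Φ{[|p1 − p0|√n − 1.96√(2p̄(1 − p̄))] / √[p1(1 − p1) + p0(1 − p0)]}.
- 2% vs 0.1%: p̄ = 0.0105, so (0.6008 − 0.2825)/0.1435 = 2.22 and power is 0.987. The continuity-corrected value is 0.977 and exact Fisher 0.997. The SAP states 98%.
- 5% vs 0.5%: power exceeds 0.9999. The SAP states >99%.

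Both figures stand.

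**2. Events.**
- Planning rates: 1,000 × 0.05 + 1,000 × 0.005 = 50 + 5 = 55. At the enrolment target of about 2,100 (SAP Section 4), 1,050 × 0.055 = 57.75.
- Low-rate scenario: 1,000 × 0.02 + 1,000 × 0.001 = 20 + 1 = 21.

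**3. Covariates.** The demographic variables are age, sex, race/ethnicity, income, urbanicity, region and insurance type: 7, taking geography as the two Section 5 items. Adding 5 scores gives 12; adding 26 diagnoses gives 38. Parameter counts depend on category numbers that the SAP does not fix. If race/ethnicity takes 4 parameters, urbanicity 2, region 3 and insurance 2 (assumed), the demographics take 14, and the totals become 19 and 45.

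**4. Events per parameter, counting treatment.**

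| Covariate terms | Parameters with treatment | 55 events | 21 events |
|---|---|---|---|
| 12 | 13 | 4.2 | 1.6 |
| 19 (assumed categories) | 20 | 2.75 | 1.05 |
| 38 | 39 | 1.4 | 0.54 |
| 45 (assumed categories) | 46 | 1.2 | 0.46 |

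**5. Chance of no control event, P = (1 − p0)^1,000.**
- 0.5%: 0.995^1,000 = 0.7%.
- 0.1%: 0.999^1,000 = 36.8%.

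With no control event the treatment coefficient has no finite maximum-likelihood estimate. Shortening the covariate list does not cure this. Fisher's test still works.

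**6. Size of the odds-ratio bias at 5% vs 0.5%.** Simulation used 2,000 subjects and 1,000 trials per setting. Covariate prevalences were assumed (1-70% for diagnoses, 2-8% for minority race levels), with no or modest covariate effects. Trials without a control event were left out of the odds-ratio summaries. The true odds ratio is (0.05/0.95)/(0.005/0.995) = 10.5, or 10.8-11.2 conditional on prognostic covariates.

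| Fit | Median OR | Geometric mean OR |
|---|---|---|
| Unadjusted | 10.7-10.9 | 11.6-11.7 |
| ML, 19 parameters | 11.1-11.6 (+6-7%) | 12.0-12.4 (+14-15%) |
| ML, 45 parameters | 11.7-14.0 (+12-25%) | 12.6-15.0 (+21-34%) |
| Firth, 19 parameters | 9.8-10.1 | 10.4-10.6 |
| Firth, 45 parameters | 9.3-10.1 | 9.8-10.6 |

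With null covariates and 19 parameters, the geometric mean is 11.7/10.5, about 12% high, before adjustment and 12.0/10.5, about 14% high, after it. So most of the excess on that scale comes from the five control events. Under other assumed covariate patterns the ML median was about 11 with 4, 19 or 45 covariates alike, about 5% high. Coverage of the 95% Wald interval was 97-98%.

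Some binary covariate level had no events in about 45-47% of trials with 19 parameters and 85-99% with 45. For example, a 1% indicator unrelated to AF has no events with probability 0.99^55 = 57.5%. This alone does not make the treatment odds ratio infinite.

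**7. Missingness rule.** The variables tested in Section 6 are demographics and co-morbidity scores. Section 7 already enters the demographics and can be read to enter the scores, so the rule adds few or no terms. It also restores no one: a subject without race or income still drops out of a complete-case fit. The documents give no missing rate. As an illustration, every 10% of subjects lost would remove about 0.10 × 55 = 5.5 events if missingness were unrelated to AF.

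**The case against.** The strongest reply is that this model is an addition. The primary Fisher's test and its >99% power do not depend on it. That stands, and it limits the weight of the point.

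A second reply is that the bias is small at the planning rates. The standard error of the log odds ratio is √(1/50 + 1/950 + 1/5 + 1/995) = 0.47. The shift in the median with 19 parameters, ln(11.1/10.5) = 0.06, is about one-eighth of that. Part of the movement with prognostic covariates is non-collapsibility, not error, and interval coverage was adequate. This also stands.

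Third, the 38-covariate reading may never apply. Section 6 and the Cox models in Section 7 speak of co-morbidity scores, which is the more natural reading of the logistic model too. But the logistic wording differs and Section 5 lists the diagnoses as covariates, so the SAP leaves the choice open.

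A reader might infer that the adjusted odds ratio is the only effect estimate for the primary outcome. The documents do not support that: the primary analysis compares two proportions, whose difference follows directly, and Section 3 plans a time-to-event comparison of the same outcome. What is missing is a stated confidence interval for the difference.

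**Conclusion.** The point holds for a supportive analysis. The event counts (55, or 21 in the low-rate scenario), the 12 to 38 named covariates and the 0.7% and 36.8% probabilities follow from the SAP. The 19- and 45-parameter figures and all simulated odds ratios rest on assumed categories, prevalences and effects.

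At the planning rates the consequence is a median odds ratio about 5-7% high with about 19 parameters. With 45 it ranges from about 5% to 25% high, depending on the assumptions. The firm defect is in the SAP's own 2% vs 0.1% case: more than one trial in three would give an infinite adjusted odds ratio, and the plan does not say what is then done.

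Two stronger readings are tempting and not supported. One is that the model will produce separation as a matter of course: for the treatment effect this is under 1% at the planning rates. The other is that the missingness rule loads many more covariates into the model: it adds few. The objection to that rule is that it is data-driven and leaves the missing values untreated.

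**What to change.** In SAP Section 7, for the adjusted model of the randomised comparison:
- Fit by Firth's penalised likelihood with profile-likelihood intervals, which gives a finite estimate even with no control event.
- Name a short covariate list in advance, for example age, sex, CHA2DS2-VASc and insurance type.
- Report the unadjusted risk difference with a 95% confidence interval beside Fisher's test.

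In SAP Section 6, for the same model, replace the missingness-significance rule with a missing category for baseline covariates, so that all randomised subjects stay in. With the short list above, little should be missing, since age and sex are needed for eligibility.

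No change to the matched cohort is asked for here. It expects 2,000 × 0.07 + 4,000 × 0.02 = 220 events at 12 months, and no such problem was shown there.

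The cost is SAP wording and one model option, with no effect on sample size or conduct. The downside is fewer covariates in a supportive model and some shrinkage toward the null. In the simulation the Firth median with 19 parameters was about 6% below the true value (9.8/10.5 and 10.1/10.8), with a geometric mean within about 2% of it. Shrinkage will be greater at very low event rates. The change should be made before outcome data are seen.

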Upon signing the informed consent document, subjects will be randomized to either the immediate monitoring group or delayed monitoring group by random number generator. The random number generator uses Ruby's pseudo-random number generator functionality (PRNG) implemented as a modified Mersenne Twister with a period of 2**19937-1. The subject's group assignment will be sent to the STSI coordinating team. Continued eligibility of all randomized subjects for the study will be confirmed upon enrollment using Aetna databases for all inclusion and exclusion criteria.

For subjects randomized to the immediate monitoring group, the first Zio patch will be sent upon confirmation of continued eligibility. The first Zio patch will be worn by subjects in the immediate monitoring group during the first two weeks of the 4-month monitoring period. A second Zio patch will be sent to subjects in the immediate monitoring group for wear during the final two weeks of the 4-month monitoring period.

A subject will be considered withdrawn from the study if they inform the STSI study coordinating center that they wish to withdraw or if they have not initiated use of the first Zio patch after 3 notifications (e-mail/phone/e-mail) from the coordinating center.

Intention-to-treat analysis for the RCT will include all participants who are enrolled in the study according to their randomly assigned group (immediate monitoring or delayed monitoring) with the RCT follow-up time for subjects in the immediate monitoring group beginning at date of enrollment and ending at 4 months following date of enrollment or the time of completion of monitoring with their final patch, whichever is longest, and for subjects in the delayed monitoring group beginning at date of enrollment and ending at 4 months following the date of enrollment.

The per protocol analysis of the RCT will include immediate monitoring participants had analyzable data from the Zio patch for at least 30 continuous minutes any time during their assigned monitoring period and all participants in the delayed monitoring group who did not withdraw from the study prior to 4 months of follow-up.

Delayed Monitoring Group

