Subjects randomized to the delayed monitoring cohort for the RCT will be actively monitored following completion of the 4 month RCT follow-up period (for which they serve as unmonitored controls). Subjects in the delayed monitoring group will receive their first Zio patch 4 months following their date of enrollment. The first Zio patch will be worn during the first two weeks of the 4-month monitoring period. A second Zio patch will be sent to subjects in the delayed monitoring group for wear during the final two weeks of the 4-month monitoring period.

Matched Observational Cohort Study: Actively Monitored (Immediate and Delayed) vs. Matched Observational Controls

For the Matched Observational Cohort study, the actively monitored group will include all subjects in the RCT who were randomly assigned to either active monitoring period (immediate or delayed).

Two matched controls will be selected for each of the 2,100 actively monitored subjects in the RCT (1,050 immediate + 1,050 delayed) from 1) the pool of subjects from the original eligible cohort who continue to be eligible based on monthly database updates and did not receive an invitation to enroll. Matching will be performed using the following criteria:

- Sex (exact)
- Age (exact by year of birth)
- CHA₂DS₂ VASc score (exact score)

CHA₂DS₂ VASc scores are re-calculated for monitored subjects at time of enrollment (updating scores calculated for eligibility of original pool). CHA₂DS₂ VASc scores are re-calculated for the pools of potential matched controls following the monthly update of the Aetna claims database and immediately prior to application of the matching protocol. Actively monitored subjects and controls will be matched on these updated CHA₂DS₂ VASc scores. Exact matches are prioritized. Matching of CHA₂DS₂ VASc score \pm 1 will be the next option if 2 exact match controls are not found for a monitored subject.

Start date for determination of outcomes from Aetna databases for both monitored subjects and matched controls will be the date of enrollment of the monitored subject. End date for the analysis of prevalence of atrial fibrillation, initiation of anticoagulation and initiation of other AF-specific interventions will be 12 months from the actively monitored subject's date of enrollment (by exact month and day). End date for analysis of outcomes at 3 years will be 3 years from the actively monitored subject's date of enrollment (by exact month and day).

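### The ITT window in SAP Section 7, read as written, follows the delayed control arm through its own patch screening to about month 8, and contradicts the arm-specific rule in SAP Section 4

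*SAP*

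**What the plan says.** SAP Section 4 (Randomized Controlled Trial Population) sets a separate window for each arm. Immediate-arm follow-up starts at enrolment, "ending at 4 months following date of enrollment or the time of completion of monitoring with their final patch, whichever is longest". The delayed-arm rule is different: "for subjects in the delayed monitoring group beginning at date of enrollment and ending at 4 months following the date of enrollment". The Delayed Monitoring Group paragraph has these subjects monitored only after "completion of the 4 month RCT follow-up period (for which they serve as unmonitored controls"). Their first patch comes 4 months after enrolment, and the second is worn in the last two weeks of the 4-month period that follows.

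SAP Section 7 (Analysis of Randomized Controlled Trial) opens with a comparison "during the first 4 months of the study between the immediate monitoring (intervention group) and delayed monitoring (control) groups". Its next paragraph defines the ITT analysis as everyone randomised to either arm, with device and claims outcomes followed "from date of enrollment to time of completion of monitoring with final patch or 4 months following enrollment, whichever is longest". That rule makes no distinction between arms.

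The per-protocol sets differ as well. Section 4 requires at least 30 continuous analysable minutes in the immediate arm and takes "all participants in the delayed monitoring group who did not withdraw from the study prior to 4 months of follow-up". Section 7 takes immediate subjects with "a Zio patch reading of a total of at least 30 minutes and all subjects randomized to the delayed monitoring group".

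**The concern.** A delayed subject's final patch falls about 8 months after enrolment. A programmer working from Section 7 would therefore keep the control arm open through both of its patches and count patch-detected AF as control events. The randomised question is screening against no screening. Under that rule it becomes earlier screening against later screening, with both arms screened by the time the outcome is counted.

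The sentence decides who counts as a case in the primary test. It also reaches the secondary analysis on the HPD definition, introduced with "Secondary analysis will be conducted using the same methods with the AF/atrial flutter endpoint defined by the HPD", because the ITT paragraph follows both analyses and is not limited to either.

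The text leaves three windows that cannot all hold: both arms to 4 months (opening of Section 7); controls to 4 months with the immediate arm possibly longer (Section 4); and both arms possibly longer (Section 7 ITT sentence).

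**Working it through.** **Dates.** First patch in the delayed arm at month 4 (SAP Section 4) plus a 4-month monitoring period gives about month 8. Protocol Section 4 starts the monitoring clock at device activation, so month 8 is the earliest planned end and any delay in activation adds to it.

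**Planned figures.** SAP Section 7 has 1,000 per arm, two-sided alpha 0.05, 5% monitored against 0.5% unmonitored, and states power above 99%. Exact Fisher power by full enumeration is above 0.999. For the SAP's low-rate case (2% against 0.1%, stated 98%), a pooled z-test gives 0.987 and exact Fisher 0.997. The plan's figures reproduce, but only with an unscreened control arm.

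**Section 7 window read literally.** The documents give no month-8 rate for the delayed arm, so its yield is an assumption. Let r be the delayed arm's screening yield relative to the immediate arm's 5%. Adding the 0.5% already diagnosed by month 4:

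control rate = 0.5% + 99.5% × 5% × r

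| r | Control rate | Difference (5% minus control) | P(Fisher p ≤ 0.05) |
|---|---|---|---|
| 0 (as planned) | 0.5% | 4.5 points | >0.999 |
| 0.25 | 1.74% | 3.3 points | 0.981 |
| 0.5 | 2.99% | 2.0 points | 0.595 |
| 0.75 | 4.23% | 0.8 points | 0.108 |
| 1 | 5.475% | −0.5 points | 0.062 |

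If the two arms simply end level, 5% against 5%, the rejection probability is 0.039. At 5% against 5.5% it is 0.064, of which only 0.005 favours screening.

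A simpler interpolation, control rate = 0.5% + u × 4.5%, shows the same pattern: 0.99, 0.71, 0.20 and 0.04 at u = 0.25, 0.5, 0.75 and 1.

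**Is equal yield too pessimistic?** SAP Section 7 expects 7% at 12 months in the two monitored arms pooled, and 2% in matched controls. Assume diagnoses outside screening accrue at the control rate: (2% − 0.5%) / 8 months = 0.1875 points per month.

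- Equal yield: immediate 5 + 8 × 0.1875 = 6.5%; delayed 5.5 + 4 × 0.1875 = 6.25%; pooled 6.375%.
- Delayed arm at only 3% by month 8: 3 + 4 × 0.1875 = 3.75%; pooled (6.5 + 3.75) / 2 = 5.125%.

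Both fall short of 7%, and equal yield comes closer. By the plan's own expectation, equal yield is not set too high.

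**Residual asymmetry in the Section 4 rule.** The immediate arm can collect claims diagnoses after month 4 while controls cannot. At a background rate between 0.5% / 4 = 0.125 and 0.1875 points per month (assumed), each month of overrun adds about 0.13 to 0.19 points, against a planned difference of 4.5. The documents do not give the lag from enrolment to activation.

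**The case against.** The strongest reply is that the intent is plain. Section 4, which defines the analysis populations, closes the delayed arm at 4 months and calls these subjects unmonitored controls. The sample-size text equates delayed monitoring with no active monitoring, and Section 7 itself opens with the first 4 months. On that reading the ITT sentence is a condensed restatement of Section 4, and a final patch within the RCT can only be an immediate-arm patch.

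Most of this stands as evidence of intent. It does not remove the conflict:

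- The ITT sentence names both arms. The device-usage paragraph just before it in Section 7 uses almost the same final-patch wording expressly for both groups.
- Section 7 is not simply Section 4 shortened: 30 minutes in total is a different criterion from 30 continuous minutes.
- Intent does not choose between the two remaining windows for the immediate arm. Its clock starts at activation, so under a strict cut 4 months after enrolment a lag of 14 days would remove the whole second patch.

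It is also fair to say that the loss of power is conditional. It arises only if the sentence is followed literally, and its size depends on r. The 12-month check sets one planning assumption against another and is not evidence of actual yield. At full yield the estimate goes slightly past zero, so bias towards no difference is an approximate description there.

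The matched-cohort per-protocol wording in Section 4 is a separate, lesser fault. It asks for patch data obtained during the RCT, when delayed subjects have none. Read narrowly it would exclude them, and it does not touch the primary test.

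**Conclusion.** The concern holds. The ITT sentence in SAP Section 7 contradicts Section 4 on when the control arm closes, 4 months or about 8, and no order of precedence is given. Followed as written, it would count control-arm screening yield in the primary outcome. The probability of a significant result would fall from above 99.9% to about 4–6% at equal yield, 11% at three-quarters, 59% at half and 98% at one quarter. These figures assume the planned 5% and 0.5% rates, 1,000 per arm and the stated range for delayed-arm yield.

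The error cannot produce a spurious benefit of screening. Because the intended rule is easy to infer and the repair is mostly wording, this is something that should be fixed and not a flaw in the design.

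**What to change.** In SAP Section 7, replace the single ITT window with the two from Section 4 and state that they govern:

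- **Delayed arm:** RCT follow-up closes 4 months after enrolment, and no patch data from this arm enter the RCT analysis.
- **Immediate arm:** follow-up closes at 4 months after enrolment or completion of the final patch, whichever is later. Amend the opening reference to the first 4 months to agree.

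Use one per-protocol definition in Sections 4 and 7, settling continuous or total minutes and the handling of delayed subjects who withdraw. In the matched-cohort per-protocol set, refer to each subject's assigned monitoring period instead of the RCT.

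Add one sensitivity analysis that cuts all data sources in both arms at 4 months from enrolment, and report the lag from enrolment to activation. Settle the wording before results by arm are seen.

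The cost is SAP text and one extra analysis. Enrolment and patch activation dates (SAP Section 2) and diagnosis dates (SAP Section 5) are already captured. Power of the primary analysis stays above 99.9%. The strict cut may lose part of the second patch in late starters. Even if half the immediate arm's yield were lost (assumed 2.5% against 0.5%), exact Fisher power for that analysis is 96%.
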